4.4 Sample size calculation

Our primary outcome of interest is a reduction in nausea, as measured by visual analogue scales (VAS). Currently, no directly comparable studies are available for an accurate sample size calculation, as previous research has not examined the effect of tVNS on nausea severity in healthy participants using VAS scores. However, a randomized controlled trial in patients with chronic nausea and vomiting due to gastroparesis or gastroparesis-like syndrome evaluated nausea improvement after either aprepitant or placebo treatment (23). This study indicated that a reduction in the mean 28-day VAS score from baseline of at least 25 mm was considered a responder. A standard deviation of 21.5 was noted in the treatment group.

The sample size calculation was based on an unpaired-sample t-test (taVNS vs. sham stimulation) with a mean difference of 25 mm and a standard deviation of 21.5. The following parameters were applied: a significance level (alpha) of 0.05 (two-sided) and a power of 0.80. Based on this calculation, we determined that 26 participants are needed. Because non-responders to nausea induction can occur, we will continue enrolment until 26 participants who meet the responder definition for nausea induction (VAS = 50 during induction) have completed the protocol. The calculation can be found at the following web address:

<https://homepage.univie.ac.at/robin.ristl/samplesize.php?test=ttest>

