8.2 Randomisation, blinding and treatment allocation

After confirming suitability for inclusion and obtaining written informed consent during the initial visit, participants will be scheduled for a second visit (referred to as the test day). Prior to this test day, an investigator will randomise the subjects in a 1:1 parallel fashion to receive either taVNS or sham stimulation. The randomisation of participants will be conducted using Castor, an electronic data capture system. The concealment list will be generated and provided to a co-worker in the same department as the coordinating investigator. For emergencies, drs. [name] will be provided with the concealment list and will be able to de-blind. The concealment list provides information on which participant will get active taVNS and who will get

sham stimulation. This information will remain confidential, and the concealment list will be sealed until after the initial analysis.

In this study, blinding procedures will be implemented. The tVNS device used will be identical for both the active and sham groups, and the ear electrodes will be placed at the same anatomical location. Furthermore, the device will blink in both groups to ensure that participants remain blinded to their treatment allocation. The key differences are that the sham group will receive a device with a non-conducting electrode, and that the electrodes for the taVNS and sham groups will be slightly different. As a result, the investigator responsible for programming the devices on the test day will be aware of treatment allocation. To maintain proper blinding for the initial analysis, the randomization code will be changed prior to the data analysis using Castor. The randomization code will be kept confidential until after the modified intention-to-treat analysis has been reported.

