The lipid infusion will be immediately halted if the participant's nausea score reaches the 50/100 threshold or if they begin retching. This is to prevent excessive discomfort. Any signs of severe nausea, such as vomiting or a participant's request to stop the procedure, will also lead to immediate cessation of the infusion.

After stopping the infusion, the nasogastric tube will be promptly removed, and participants will then receive either taVNS or sham stimulation for 30 minutes. During this stimulation phase, the severity of nausea will be assessed using a 0-100 VAS score, where 0 signifies "no nausea" and 100 represents "the worst nausea imaginable". VAS scores will be recorded every 5 minutes, continuing for 30 minutes post-stimulation to evaluate the efficacy of taVNS in alleviating nausea. VAS scores

for other gastrointestinal symptoms will also be recorded at the same time points as nausea severity. Additionally, VAS scores for the desire to eat will be recorded at four specific time intervals.

Plasma levels of ghrelin and motilin and salivary cortisol will be measured on four different time points: baseline, at the end of nausea induction, immediately after the taVNS vs. sham stimulation, and 60-minutes post-nausea induction.

Autonomic parameters, including heart rate variability and skin conductance, will be continuously recorded from the onset of nausea induction until 30 minutes after either taVNS or sham stimulation. These measurements will be captured using a Shimmer3 GSR sensor and Fitbit smartwatch, as was previously utilized in other studies within our department (NL87188.068.24/METC 24-029). The Shimmer3 GSR sensor, a CE-certified device (see K6.6_Shimmer_CE_Certificate_of_conformity_Versie1.0_dd 04-09-2014) will be used to collect data on heart rate variability and skin conductance. The Fitbit wearable device will be used to collect participant data concerning HRV. The device will be connected to the coordinating investigator's smartphone via Bluetooth and the Fitbit app. Heart rate data will then be automatically collected by the Fitbit.

Once all measurements are completed, the tVNS device, intravenous cannula, Shimmer, and Fitbit will be removed.

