The BFI is an instrument designed to assess the personality of individuals aged 18 and above. It comprises 44 items divided into five sub-scales, each representing one of the five personality factors: extraversion (8 items), neuroticism (8 items), conscientiousness (9 items), agreeableness (9 items), and openness to experience (10 items). Participants are required to rate the extent to which they agree with the statement using a 5-point Likert scale ranging from 1 (Disagree strongly) to 5 (Agree strongly) (53). During the initial visit, participants will complete the BFI to evaluate their personality traits.

0-10 Visual Analogue Scale (VAS) – Nausea**‘F1.5_VAS_Scales_Versie1.0_dd 10-10-2024’**

Participants will be requested to assess the severity of nausea at regular time intervals following nausea induction and either taVNS or sham stimulation. The score will range from 0 to 100, where 0 indicates ‘no nausea’ and 100 indicates ‘the worst nausea imaginable’. In total, 14 questionnaires will be completed: one at baseline (pre-infusion), one immediately after stopping the lipid infusion (when the predetermined nausea score of 50/100 is reached), at six time points during stimulation at 5-minute intervals, and at six time points in the post-stimulation phase at 5-minute intervals.

0-10 Visual Analogue Scale (VAS) – Other gastrointestinal symptoms**‘F1.5_VAS_Scales_Versie1.0_dd 10-10-2024’**

Participants will be asked to assess the severity of additional gastrointestinal symptoms, including abdominal pain, bloating, and fullness. They will provide a score ranging from 0 to 100, where 0 indicates ‘not at all’ and 100 indicates ‘extremely severe’. These symptoms will be evaluated at the same 14 time points as for nausea severity.

0-10 Visual Analogue Scale (VAS) – The desire to eat**‘F1.5_VAS_Scales_Versie1.0_dd 10-10-2024’**

Participants will be asked to assess their desire to eat by providing a score on a scale from 0 to 100, where 0 indicates ‘no desire to eat at all’ and 100 indicates ‘extremely strong desire to eat’. This will be evaluated at four time points: at baseline (pre-infusion), immediately after stopping the lipid infusion, after taVNS or sham stimulation, and at the end of the post-stimulation period.

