8.5 Replacement of individual subjects after withdrawal

We accounted for potential dropouts in our sample size calculation.

If a subject decides to discontinue participation before completing all study procedures, this subject will be considered a dropout and will be excluded from analyses. In case this happens during the recruitment period of the study,

researchers may choose to replace the subject. However, subject IDs will not be reused to prevent data confusion; instead, a new subject ID will be assigned to the “replacing” participant.

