10. STATISTICAL ANALYSIS

Demographic data and patient-reported data will be collected and saved in Castor EDC. Database cleaning will be carried out by internal consistency checks and identification of database entries outside expected ranges by the study coordinator and the local research nurses. Primary and secondary outcomes will be analyzed based on a modified intention-to-treat (ITT) approach. SPSS, R, Python, and Excel will be used to perform the statistical analysis.

Subject characteristics will be presented and analysed using descriptive statistics. Continuous parameters will be presented as means and standard deviations, and assessed between the two groups (taVNS vs. sham) with a two-sample unpaired t-test (for normally distributed data) or a nonparametric Mann-Whitney U test (for non-normally distributed data). Categorical variables will be represented as frequencies and analyzed using a Chi-square test or a Fisher's exact test. A p-value < 0.05 will be considered statistically significant. No missing data are expected; however, if present, missing data will be handled using appropriate statistical methods.

The modified intention-to-treat population will be defined as all randomized participants who successfully complete the nausea induction procedure and in whom the intervention (taVNS or placebo) is initiated. All primary and secondary outcome analyses will be conducted based on this analysis set.

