10.1 Primary study parameter(s)

To assess the effect of taVNS on nausea severity, Visual Analogue Scale (VAS) scores will be compared at various timepoints following nausea induction between the taVNS and sham stimulation groups. A linear mixed-effects model (LMM) will be utilized to evaluate both intergroup differences and within-group changes in VAS scores over time. LMM offers flexibility by adjusting for baseline nausea severity (if needed), handling missing data, and accounting for individual variability through random effects. LMM uses all available data points for each individual in likelihood estimation, rather than excluding participants with missing data. If LMM assumptions are violated, a nonparametric alternative may be considered. Potential confounding factors will be included as covariates in the LMM to adjust for their effects. Differences in VAS scores will be reported along with their corresponding 95% confidence intervals (CIs) and two-sided p-values, using a significance level (type I error rate) of 0.05.

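### Section 8.5 drops voluntary early leavers from the analyses, which contradicts the modified intention-to-treat set in Section 10 and the all-available-data model in Section 10.1

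*Protocol*

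**What the plan says.** The Protocol has two rules for a subject who does not finish the test day.

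- **Section 8.5 (replacement after withdrawal):** if a subject "decides to discontinue participation before completing all study procedures, this subject will be considered a dropout and will be excluded from analyses". The sentence has no limit on when the subject leaves or on which analyses are meant. Replacement is optional.
- **Section 10 (statistical analysis):** the modified intention-to-treat set is "all randomized participants who successfully complete the nausea induction procedure and in whom the intervention (taVNS or placebo) is initiated", and "All primary and secondary outcome analyses will be conducted based on this analysis set". Completing the protocol is not a condition.
- **Section 10.1 (primary parameter):** "LMM uses all available data points for each individual in likelihood estimation, rather than excluding participants with missing data".

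The blinding text points the same way as Section 10. Section 8.2 says "The randomization code will be kept confidential until after the modified intention-to-treat analysis has been reported", and Sections 3 and 5.1.2 say the same. No sentence states which rule prevails.

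**The concern.** The analysis set for the primary comparison is fixed in two incompatible ways. Three groups are not affected: subjects who leave before stimulation, subjects who do not respond to induction (both outside the modified intention-to-treat set anyway), and subjects withdrawn by the investigator under Section 8.4, since Section 8.5 speaks only of a subject who decides to leave. What remains is the participant who starts taVNS or sham and chooses to go during the 30 minutes of stimulation or the 30 minutes after it.

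For that participant, Section 8.5 discards ratings already recorded and turns the analysis into one of completers. If leaving is linked to nausea, and more so in one arm than the other, the arms being compared are no longer those formed by randomisation. Section 4.4 says "we will continue enrolment until 26 participants who meet the responder definition for nausea induction" have completed the protocol. That restores the number analysed but not the comparability, because a leaver is replaced by someone who stayed. If the choice between the rules is left open, it may be made once it is known who left.

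**Working it through.** **Step 1. The plan's own figure.** Section 4.4 assumes a difference of 25 mm, SD 21.5, two-sided alpha 0.05 and power 0.80. A two-sample t-test (noncentral t) needs 12.65 per arm, so 13 per arm and 26 in total, with power 0.812. The stated 26 reproduces.

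**Step 2. One subject under both rules.** Take a subject who reaches the induction threshold, receives the full 30 minutes of stimulation and then leaves.

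- Section 8.3.4 schedules nausea ratings at baseline, at the end of infusion, and "at six time points during stimulation at 5-minute intervals, and at six time points in the post-stimulation phase at 5-minute intervals". Recorded: 1 + 1 + 6 = 8 of 14, of which 6 of the 12 taken after stimulation starts.
- The Section 8.3.2 schedule reads "salivary cortisol will be measured on four different time points: baseline, at the end of nausea induction, immediately after the taVNS vs. sham stimulation"; the fourth and last sampling time falls one hour after induction, and blood is drawn on the same schedule as saliva. Recorded: 3 of 4 blood and 3 of 4 saliva samples.
- Desire to eat (Section 8.3.4): 3 of 4 ratings.

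Sections 10 and 10.1 keep all of this. Section 8.5 discards all of it.

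**Step 3. Size in a worst case.** The protocol gives no number of withdrawals, so what follows is assumption:

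- no true effect;
- total SD 21.5 mm at each rating (the Section 4.4 value, borrowed from another trial);
- within-subject correlation ρ of 0.5 or 0.8;
- 13 completers per arm, with one arm starting with 13 + k subjects;
- the k subjects of that arm with the highest mean nausea during stimulation leave after rating 6 of 12;
- VAS limits of 0 and 100 not imposed.

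The simulation used 8,000 runs per case, with Monte Carlo SE 0.07 to 0.08 mm. The standard error (SE) of the contrast of 12-rating means is 21.5 × √(ρ + (1 − ρ)/12) × √(2/13), which is 6.21 mm for ρ = 0.5 and 7.62 mm for ρ = 0.8.

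| Leavers k | ρ | Shift, completers only | Share of 25 mm | Shift ÷ SE |
|---|---|---|---|---|
| 1 | 0.5 | 2.07 mm | 8.3% | 0.33 |
| 1 | 0.8 | 2.56 mm | 10.2% | 0.34 |
| 2 | 0.5 | 3.45 mm | 13.8% | 0.56 |
| 2 | 0.8 | 4.45 mm | 17.8% | 0.58 |

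*Analytic check, k = 1, ρ = 0.5.* The expected maximum of 14 standard normal values is 1.703, so removing it lowers the mean of the other 13 by 1.703/13 = 0.131 SD. The SD of a six-rating mean is 21.5 × √(0.5 + 0.5/6) = 16.42 mm, which gives 0.131 × 16.42 = 2.15 mm during stimulation. The post-stimulation phase inherits the fraction 0.5/(0.5 + 0.5/6) = 0.857 of that, or 1.84 mm. The average is 2.00 mm, which agrees with the simulated 2.07 within Monte Carlo error.

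Under the same assumptions, a likelihood-type model on all available data gave shifts of 0.07, 0.03, −0.05 and 0.03 mm. That is expected by construction: leaving depends only on recorded ratings and the fitted model is the true one.

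**Step 4. Direction.** If the most nauseated leave the sham arm, excluding them hides a benefit. If they leave the taVNS arm, it exaggerates one. If leaving is similar in both arms and there is no true effect, the shifts cancel in expectation.

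**The case against.** **Section 10 plainly governs.** Section 8.5 is an administrative paragraph on replacement and subject numbers. Section 10 defines the analysis set, and three other sections name the modified intention-to-treat analysis. An analyst would probably follow Section 10. This is fair, and it marks Section 8.5 as the sentence to change. It does not remove the conflict, because nothing gives Section 10 precedence.

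**Dropout here means failed induction.** Sections 5.2.1 and 8.3.2 use the word that way. But those test days are terminated for the subject, whereas Section 8.5 concerns a subject who decides to leave at any point before all procedures are done, which includes the post-stimulation ratings.

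**The case is rare.** It needs a voluntary departure within one supervised hour, after the infusion has stopped and the tube is out. Apart from induction non-responders, the 150 euros goes to those who complete (Section 11.6). Severe nausea is treated with ondansetron (Section 5.3), and Section 10 expects no missing data. This stands and limits the weight of the point. Section 8.4 still lets subjects leave at any time.

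**The magnitude is a constructed extreme.** This also stands. All leavers are put in one arm and are its most nauseated. The SD comes from the treatment group of a trial in chronic nausea and is applied to each rating in healthy subjects who start near 50. The shift scales directly with it. Even then it is 0.33 to 0.58 of a standard error, with a simulated false-positive rate of about 7% for one leaver and 10 to 11% for two. If leaving depended on unrecorded nausea, the all-available-data model would be biased too.

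**Stronger readings that the documents do not support.** A reader might infer that early leavers disappear from safety reporting. Sections 9.2 and 9.4 have adverse events recorded, reported and followed, so no safety gap follows from Section 8.5. A reader might also infer a loss of power, but the count of completers is protected by the Section 4.4 enrolment rule. Nor do the documents show that the result will be biased, since they give no number or pattern of withdrawals.

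**Conclusion.** The contradiction is real and stands in current text. It is not something left to a statistical analysis plan, because the Protocol itself fixes both rules. It reaches only subjects who choose to leave after stimulation has started. For them, Section 8.5 would produce a completers-only analysis with selection after randomisation.

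The size depends on withdrawals that the Protocol does not quantify. It is zero if nobody leaves in that window and near zero in expectation if leaving is similar in both arms with no true effect. In the one-arm worst case, under the borrowed SD and assumed correlations, it is about 2 to 4.5 mm, or 8 to 18% of the planned 25 mm. The sentence should be corrected because it is wrong as written and cheap to repair, not because a large bias is expected.

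**What to change.** Replace the exclusion in Section 8.5 with wording such as: *A subject who discontinues may be replaced; data collected up to discontinuation are analysed according to the Section 10 modified intention-to-treat set.* Make the change before the randomisation code is released, so that the rule is not chosen after it is known who left.

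The cost is one reworded sentence. It needs no extra participants, visits or measurements, and the Section 10.1 model already accommodates incomplete series. One condition applies: the consent form is not among the documents reviewed, so the sponsor should confirm that it allows data already collected to be used after voluntary withdrawal. No change to Section 8.6 or to the safety sections is needed for this point.

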8.6 Follow-up of subjects withdrawn from treatment

Subjects withdrawn from the study will not be followed up unless it seems necessary in case of any urgent medical reason.

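### Section 8.5 excludes from analysis participants whom Section 10 keeps: those who start stimulation and then choose to stop before the last assessment

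*Protocol*

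**What the plan says.** Section 8.5 deals with replacement after withdrawal. Its condition is "If a subject decides to discontinue participation before completing all study procedures", and its consequence is that "this subject will be considered a dropout and will be excluded from analyses". If this happens during recruitment, "researchers may choose to replace the subject". The same section opens with the statement "We accounted for potential dropouts in our sample size calculation".

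Section 10 defines the mITT population as "all randomized participants who successfully complete the nausea induction procedure and in whom the intervention (taVNS or placebo) is initiated" and adds: "All primary and secondary outcome analyses will be conducted based on this analysis set". Completing the later assessments is not part of that definition. On the primary model, Section 10.1 says: "LMM uses all available data points for each individual in likelihood estimation, rather than excluding participants with missing data".

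Two other places bear on this. Section 8.6 says "Subjects withdrawn from the study will not be followed up", except where an urgent medical reason makes it necessary. Section 4.4 derives 26 participants from an unpaired t-test and then continues enrolment until 26 induction responders have completed the protocol.

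**The concern.** Whether a given participant enters the primary analysis depends on which section the analyst follows, and nothing in the protocol says which prevails. A separate analysis plan may exist, but this is not a detail left for it to supply: the protocol fixes both rules, and they disagree.

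The trial induces nausea and then measures it. Leaving after stimulation has begun happens after randomisation and may be related to how nauseous the participant is. If such people are removed, the comparison is between those who stayed, and randomisation no longer protects it. Replacing them restores the number of participants but does not undo the selection. Because 8.6 provides no routine follow-up, the readings taken before exit are the only efficacy data from these participants, and 8.5 would discard them.

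The opening sentence of 8.5 is a second, smaller problem. It tells the reader that the calculated sample size already contains a margin for dropouts.

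**Working it through.** **1. Who is affected.** Compare the two rules by the time at which a participant chooses to stop.

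- Before or during induction, or without reaching the induction threshold: outside the mITT set under Section 10, and excluded under 8.5. No conflict.
- After stimulation starts but before the last reading: inside the mITT set under Section 10, excluded under 8.5. Conflict.
- After all procedures: included under both. No conflict.

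Section 8.3.4 lists 14 nausea readings: baseline, end of infusion, six during stimulation and six after it, at 5-minute intervals. The window of conflict is therefore 12 × 5 = 60 minutes. As an example, someone who leaves after the eighth of those 12 readings has 2 + 8 = 10 of 14 readings on file. Section 10.1 uses the available ones; 8.5 uses none.

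**2. The plan's sample size.** Inputs from Section 4.4: difference 25 mm, SD 21.5, two-sided alpha 0.05, power 0.80; 1:1 allocation from Section 3. For n per arm, the noncentrality is 25 / (21.5 × √(2/n)) on 2n − 2 degrees of freedom.

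- n = 12: 25 / (21.5 × 0.408) = 2.85, df 22, power 0.777.
- n = 13: 25 / (21.5 × 0.392) = 2.96, df 24, power 0.812.

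The smallest n that reaches 0.80 is 13, so the total is 26. The plan's figure is reproduced exactly with no dropout inflation. Inflating it would have given 26 / 0.95 → 28 for 5% loss, 26 / 0.90 → 29 for 10%, or 26 / 0.80 → 33 for 20%.

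**3. Power if 8.5 is applied and nobody is replaced.** Same t-test, with losses split as evenly as possible between arms:

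- 1 lost: 0.794
- 2 lost: 0.777
- 3 lost: 0.757
- 4 lost: 0.737

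If enrolment continues to 26 completers, this loss does not arise and only the selection remains.

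**4. How far selection could go (assumed, not from the protocol).** Suppose there is no true effect, scores are normal with SD 21.5, and the k highest of 13 scores are removed from one arm only. Simulation with 100,000 trials gave:

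- k = 1: that arm's mean falls by 3.0 mm (3.0 / 25 = 12% of the planning difference); type I error about 0.07.
- k = 2: 5.5 mm (22%); about 0.11.
- k = 3: 7.9 mm (32%); about 0.16.

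This is a severe pattern, since it takes exactly the worst scorers and all from one arm. If both arms lose participants in the same way, the expected shift in the difference is zero.

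**The case against.** **The conflict is narrow.** A reader might take 8.5 to remove anyone who stops. It does not: it speaks of a subject's own decision, and withdrawal by the investigator under 8.4 is not expressly covered. The exits at issue fall within about an hour under supervision. By then the infusion has ended, the tube is out and nausea is expected to subside (8.3.2). Payment goes to those who complete the study (11.6), and Section 10 expects no missing data. Few participants, perhaps none, may be affected. All of this stands and limits the size of the problem, but it does not reconcile the two rules.

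**The link to bad outcomes is inferred.** A reader might conclude that 8.5 discards the participants with the worst nausea and so biases the result in a known direction. The protocol foresees vomiting and escape medication (5.3, 8.3.2), but severe nausea is not a withdrawal trigger and no dropout rate or reasons are given. Direction depends on which arm loses more people. Likewise, 8.5 does not say who decides on replacement, so the idea that someone aware of allocation would choose is only an inference from the unblinded device programming in 8.2.

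**Losses are provided for.** Enrolling until 26 responders have completed is a real safeguard for numbers, and it makes the optional replacement wording less important. It is not an allowance inside the calculation. One could also note that the normal approximation gives 12 per arm, and 24 / 0.95 rounds up to 26. But 4.4 names the t-test and lists no dropout rate among its inputs.

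**Section 10 is the specific text.** The mITT analysis is also named in Sections 3, 5.1.2 and 8.2, whereas the exclusion stands only in a section on replacement. An analyst would probably follow Section 10. That supports a moderate rating, but leaving the choice to the analyst is what the plan should avoid.

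**Conclusion.** The contradiction is real. For participants who start stimulation and then choose to stop, Section 10 requires inclusion and 8.5 requires exclusion. The statement that the calculation allowed for dropouts is also unsupported: 26 is the uninflated t-test size, and continued enrolment under 4.4 is the only provision for losses.

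The effect on the result cannot be determined from the protocol. If one or two exclusions are unrelated to outcome and not replaced, power moves only from 0.81 to 0.79 or 0.78. If they were the highest scorers and all in one arm, the shift would be about 3.0 to 5.5 mm and type I error about 0.07 to 0.11; that rests on the assumptions in step 4. The documents therefore do not support saying that the randomised comparison will be broken, only that 8.5 would allow it to be weakened in a trial with 13 per arm.

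Keeping these participants is not a complete remedy either. With no routine follow-up, the model has only their readings up to exit.

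This should be fixed, and before data are seen, because it decides who enters the primary analysis.

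**What to change.** In Section 8.5:

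- Delete the clause that excludes these subjects from analyses.
- State that anyone in whom stimulation was initiated stays in the mITT set with all VAS readings recorded up to discontinuation.
- State that participants added later supplement them and do not substitute for them. The mITT set may then exceed 26.
- Replace the opening sentence on dropouts with: *26 includes no dropout inflation; losses are handled by continued enrolment as in 4.4.*

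The cost is a few sentences in one section. It needs no new data or procedures and leaves the target of 26 unchanged.
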